## **9.0 Study Population**

9.1 Inclusion Criteria:

Primary Care Providers:

The final study sample for outcomes derived from EHR and PMP data will include all PCPs from all of the Fairview and UMP study clinics.

Retrospective chart reviews of primary care visits with current opioid users:

1. Male or female  $\geq 18$  years of age at the primary care visit
2. Current "high-risk" opioid user as defined by having a current opioid prescription with at least 50 MME/day and/or having a current opioid prescription along with a current benzodiazepine prescription.

9.2 Exclusion Criteria:

Primary Care Providers:

PCPs will be excluded from the final analytic sample if they work less than 20% FTE.

Retrospective chart reviews of primary care visits with current opioid users:

Patient records corresponding to each PCP will only be included in the analysis if the patient has Minnesota Research Authorization.

9.3 Screening:

Information on which PCPs work in the study clinics will be provided by staff from Fairview and UMP. Information on which patient records have Minnesota Research Authorization will be provided by the AHC IE staff.

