## **11.0 Number of Participants**

### **11.1 Number of Participants to be Consented:**

We expect to enroll approximately 300-350 PCPs in both the baseline and follow-up web surveys.

We expect that 400-450 PCPs will be included in the final analytic samples for the analysis of EHR data and PDMP data.

We expect that 20,000 charts will be reviewed in the retrospective chart reviews of primary care visits with current opioid users.

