### Futility Analysis

There will be no formal futility analyses presented to the DMC. Given that these interventions have small potential adverse effects, the DMC will NOT be asked to recommend early termination for futility.

17.2 Power Analysis: The proposed design has sufficient power to detect clinically meaningful changes in opioid prescription practices from the main effects of the two interventions and the control group (10). All power calculations assume a two-sided test at the 0.05 significance level. Power for the Primary Aim (comparison of intervention arms to the control during months 1-6) is shown in Exhibits 2a-b assuming a total of 48 clinical are randomized (equal allocation between Arms 1-4) with a conservative estimate of 10 providers per clinic (~12 providers per clinic in the FHS/UMP system). The range of the number of visits eligible and the percentage of visits with an opioid prescription in the control arm (for both the opioid-naïve and opioid-using populations) were based on preliminary data from the EHR from a subset of clinics that will be randomized. Meeker et al. (1) assumed an intra-clinic correlation of 0.05 but that encounters within the same provider were not further correlated. We assumed the correlation for visits within the same clinic (but with different providers) was 0.025 and the within-provider correlation would be 0.075 as well as considering a more conservative scenario (correlation given on the logistic scale (11)). We assumed a 5% and 17% prescription rate in the control arm for the opioid-naïve and opioid-using populations, respectively, based on preliminary analysis of opioid prescribing in Fairview primary care clinics, and based on published research (12). We considered a difference in the percentage of eligible encounters with an opioid prescription between the intervention and control groups of 3.5% and 5% to be of clinical interest in the two populations. Exhibits 8 and 9 demonstrate that we have sufficient power across a wide range plausible scenarios and maintain adequate power even under smaller effect sizes. These calculations are also conservative as they assume 48 clinics, whereas we expect to enroll over 50 clinics.

We also have sufficient power to detect differences between 2.5 to 4 percentage points across the two intervention sets during the first 6 months of the intervention.

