## 26.0 Resources Available

### 26.1 Resources Available:

- This project is funded by an R33 grant from NIDA, over a three year period. The PI's project time is funded at 30% FTE for all three years. All co-Investigators are funded at levels from 5%-15% FTE over the three year period. There is also a 50% FTE Project Manager and a 50% FTE doctoral student research assistant.
- For the primary outcomes, we will have EHR data on all of the PCPs who are working in the study clinics. We expect this will include approximately 400 PCPs. For the web survey component, we expect a 75% response rate.
- The research team has all of the required statistical software and computing resources needed to complete the research, including departmental resources and the AHC-IE's resources.
- All people assisting with the research will be required to undergo training in the research background, objectives, and procedures. The PI will be responsible for clearly delineating all duties and functions of the entire research team.

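### Section 17.2 calls 10 providers per clinic conservative, but 48 × 10 = 480 is 7–20% above the 400–450 PCPs the protocol expects to analyse

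*Combined protocol and SAP*

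**What the plan says.** The power paragraph (section 17.2) takes 48 clinics, split evenly over the four arms. For clinic size it uses this figure: "conservative estimate of 10 providers per clinic (~12 providers per clinic in the FHS/UMP system"). It adds a second claim of caution: "These calculations are also conservative as they assume 48 clinics, whereas we expect to enroll over 50 clinics". The comparison is the "comparison of intervention arms to the control during months 1-6", and "All power calculations assume a two-sided test at the 0.05 significance level".

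Two other sections give the number of providers expected in the data. Section 11.1: "We expect that 400-450 PCPs will be included in the final analytic samples for the analysis of EHR data and PDMP data". Section 26.1, on EHR data for the primary outcomes from all PCPs working in the study clinics: "We expect this will include approximately 400 PCPs". Section 9.2 adds an exclusion: "PCPs will be excluded from the final analytic sample if they work less than 20% FTE".

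Exhibit 8 prints power for reductions of 15, 20, 25 and 30% from a 7% control rate: 96, 100, 100 and 100% at 30 eligible visits per provider per month, and 76, 95, 100 and 100% at 15. Its caption gives no clinic or provider count. Exhibit 9 states its own size, 40 clinics with 10 providers each.

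**The concern.** An input is conservative for power if the truth is expected to be more favourable. Here the provider total in section 17.2 is higher than either of the protocol's own expectations, so the label points the wrong way. The benchmark offered for it, about 12 per clinic, would imply 12 × 48 = 576 providers, which is further still from 400–450. The 20% FTE exclusion may explain part of the gap, but a power calculation should use the count after exclusions. No section reconciles the figures.

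At stake is how a reader takes the least favourable cell of Exhibit 8, a 15% reduction at 15 visits per month. It is printed at 76%, already below 80%, and the label suggests that actual power is higher. It also leaves the two exhibits on different provider totals if Exhibit 8 follows the text: 480 against 400.

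**Working it through.** **Step 1. Provider counts (no modelling).**
- Assumed in 17.2: 48 × 10 = 480.
- Expected in 11.1: 400–450, so 400/48 = 8.3 to 450/48 = 9.4 per clinic. At 50 clinics, 400/50 = 8.0 to 450/50 = 9.0, and fewer above 50.
- Excess of the assumed total: 480/450 = 1.07 and 480/400 = 1.20, i.e. 7% to 20%.
- Exhibit 9: 40 × 10 = 400, which agrees with 11.1 and 26.1.

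**Step 2. Reproducing Exhibit 8.** The documents give no formula, so this is a reconstruction. Inputs: 12 clinics per arm (48/4), 10 providers, 15 or 30 visits per month, control rate 7% (caption), 6 post-months (17.2), 12 pre-months (17.3), two-sided 0.05.

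Effect: logit(0.07) − logit(0.0595) = 0.174 for a 15% reduction; 0.238 for 20%.

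SE = √[ 2 / (12 × providers × visits × 0.07 × 0.93) × (1/6 + 1/12) ]; power = Φ(effect/SE − 1.96).

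For the 76% cell with 10 providers, SE = 0.0653, 0.174/0.0653 = 2.66, and power = Φ(0.70) = 75.8%. With 400/48 = 8.33 providers, SE = 0.0716, the ratio is 2.43, and power = Φ(0.47) = 68.0%.

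| Cell | Printed | 480 PCPs | 450 PCPs | 400 PCPs |
|---|---|---|---|---|
| 15% reduction, 30 visits | 96% | 96.4% | 95.4% | 93.0% |
| 15% reduction, 15 visits | 76% | 75.8% | 73.1% | 68.0% |
| 20% reduction, 15 visits | 95% | 95.4% | 94.2% | 91.4% |

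**Step 3. Two cross-checks.**
- A pre/post logistic model with clinic and provider random intercepts (logistic-scale correlations 0.025/0.075, common baseline) gives 95.8, 74.6 and 94.4% at 480; 94.6, 71.9 and 93.1% at 450; and 92.0, 66.9 and 90.1% at 400. A 25% reduction at 15 visits goes from 99.5% to 98.5% at 400. Spreading the same PCPs over 52 clinics changes these figures by 0.1 point at most.
- Scaling the printed powers, Φ[(1.96 + z_power) × √(N/480) − 1.96], takes 76% to 73.3% (450) and 68.2% (400), 96% to 94.9% and 92.3%, and 95% to 93.7% and 90.8%.

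The three routes put the 76% cell at about 67–73%. They put the 96% and 95% cells about 1–5 points below print.

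**Step 4. Does the match prove that Exhibit 8 used 480?** No. The formula depends only on total provider-months. A 20 v 20 layout with 10 providers per clinic (400 PCPs in 40 clinics), 6 post-months and an assumed 4 pre-months has the same information: (20 × 10)/(1/6 + 1/4) = 480, against (12 × 10)/(1/6 + 1/12) = 480. It gives the identical 96.4, 75.8 and 95.4%.

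**Step 5. The planned primary analysis.** Section 17.3 pools two arms against two. Replacing 12 by 24 clinics per group, with 400 PCPs in all, the 76% cell becomes 0.174/0.0506 = 3.43, so Φ(3.43 − 1.96) = 93.0%. At 0.025, the level under the Bonferroni correction across the two populations, it is 88.3%. The other two cells are at least 99.3% at either level.

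**The case against.** The other side accepts the count mismatch and disputes what follows from it.

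*Attribution.* The sentence with 48 × 10 points to Exhibits 2a-b, Exhibit 8's caption gives no sample size, and Exhibit 9 departs from the 48 in the text. A reader might infer that Exhibit 8's lower entries are simply overstated. The documents do not establish that. Taking 48 × 10 as the basis of Exhibit 8 is the natural reading, since the same paragraph later cites Exhibits 8 and 9 and says that the calculations assume 48 clinics, but Step 4 shows that the printed values cannot confirm it. This stands, and it makes the power figures conditional.

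*Consequence.* A reader might also infer that the trial is underpowered. Step 5 shows otherwise for the pooled analysis. Section 17.2 names a difference of 3.5 percentage points as of interest in opioid-naïve patients. Against 7% that is a 50% reduction, beyond the last column of Exhibit 8, and power at 400 PCPs is about 100% even for the one-arm contrast. This stands.

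*Visits.* PCPs under 20% FTE presumably contribute few visits, so excluding them may cut visits less than proportionally. At 400 PCPs, 15 × 480/400 = 18 visits per month would restore the total, within the exhibit's 15–30 range. This is plausible, but the plan does not argue it.

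*Other inputs.* The text of 17.2 gives a 5% opioid-naïve rate, not 7%. At 5% with 480 PCPs the formula gives 61% for the 76% cell, a larger shift than the provider count causes. This is a good reason not to print replacement figures from an inferred formula.

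None of these objections makes 10 per clinic a conservative input.

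**Conclusion.** The inconsistency holds on the documents' own numbers: the provider total behind 17.2 is 7–20% above the expected analytic sample, and calling 10 per clinic conservative is wrong as written.

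The effect on power is conditional. It assumes that Exhibit 8 rests on 48 × 10, that it compares one arm with control using 12 pre- and 6 post-months, and that the 7% rate and visits per provider are unchanged. On that basis the 76% entry becomes about 67–73%, the 96% and 95% entries lose about 1–5 points, and reductions of 25% or more keep about 98.5% or above. The only cell that moves materially was already printed below 80%.

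The point supports no claim that the pooled primary analysis lacks power. Since all PCPs in the clinics are included, no recruitment target depends on this input. Severity: minor.

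**What to change.** In 17.2, replace 48 × 10 with the expected analytic count after the FTE exclusion (400–450 PCPs), in agreement with 11.1 and 26.1, and delete the word conservative for providers per clinic. Have the sponsor's statistician recompute Exhibit 8 at that count by the original method. The caption should state the contrast (one arm versus control, or pooled), the pre- and post-periods, the numbers of clinics and providers, and the control rate. The figures reconstructed here should not be printed as replacements.

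The cost is one restated sentence and one table, with slightly less favourable power if the printed contrast is kept. No clinics, PCPs or data collection are added.

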Exhibit 8. Power to detect a difference in proportion of eligible visits with an opioid prescription between intervention and control arms. Power calculations assume an opioid prescription rate in the no intervention arms of 7%.									
30 eligible visits/month/provider					15 eligible visits/month/provider				
	% reduction in opioid prescribing					% reduction in opioid prescribing			
Intra-clinic/ Intra-provider correlation	15%	20%	25%	30%	Intra-clinic/ Intra-provider correlation	15%	20%	25%	30%
0.025/0.075	96%	100%	100%	100%	0.025/0.075	76%	95%	100%	100%

Exhibit 9. Power to test a difference in proportion of eligible visits resulting in an opioid prescription between intervention and controls arms in opioid-using population (Primary Aim). Power calculations assume 40 clinics randomized equally to Arms 1-4 with 10 providers/clinic, the opioid prescription rate in the control arm was 17%.									
10 eligible visits/month/provider					5 eligible visits/month/provider				
	Difference in opioid prescription rate between control and intervention					Difference in opioid prescription rate between control and intervention			
Intra-clinic/ Intra-provider correlation	4.5%	5%	5.5%		Intra-clinic/ Intra-provider correlation	4.5%	5%	5.5%	
0.025/0.075	81%	89%	95%	0.025/0.075		77%	86%	93%	

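### The claim of sufficient power for 2.5 to 4 point differences between the two intervention sets is not supported for current opioid users under the plan's own assumptions

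*Combined protocol and SAP*

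**What the plan says.** The power section (17.2) of the combined protocol and SAP sets common assumptions:

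- Test: "All power calculations assume a two-sided test at the 0.05 significance level".
- Primary Aim: "comparison of intervention arms to the control during months 1-6".
- Size: "assuming a total of 48 clinical are randomized (equal allocation between Arms 1-4"), with 10 providers per clinic.
- Correlation: "We assumed the correlation for visits within the same clinic (but with different providers) was 0.025 and the within-provider correlation would be 0.075", with the "correlation given on the logistic scale".
- Control prescribing rates: 5% (opioid-naive) and 17% (opioid-using). The differences of interest are 3.5 and 5 points respectively.

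The text of 17.2 closes with the claim at issue: "We also have sufficient power to detect differences between 2.5 to 4 percentage points across the two intervention sets", for the first six months. No exhibit tabulates that contrast.

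Exhibit 9 is the only table for opioid users. Its caption reads "Power calculations assume 40 clinics randomized equally to Arms 1-4 with 10 providers/clinic, the opioid prescription rate in the control arm was 17" (per cent). It compares intervention with control. For differences of 4.5, 5 and 5.5 points it prints 81%, 89% and 95% power at 10 eligible visits per provider per month, and 77%, 86% and 93% at 5.

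Section 17.3 fits a separate model for each intervention, pooling two factorial arms against the other two. It describes no model comparing set A (choice architecture) with set B (PMP integration).

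**The concern.** Exhibit 9 starts at 4.5 points, where power is already only 77-81%. Under the same assumptions any smaller difference has less. Yet the closing sentence claims sufficient power for 2.5 to 4 points without limiting itself to a population, and a direct comparison of A with B would use fewer clinics than Exhibit 9 does.

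The two populations are analysed separately, so a power statement that covers both without naming either has to hold for each. If it fails for current users, a reader who sets the A and B results side by side in that group could take a null difference as well powered when it was not.

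**Working it through.** **Inputs.** From 17.2 and Exhibit 9: two-sided alpha 0.05; correlations 0.025 (clinic) and 0.075 (provider) on the logistic scale; 10 providers per clinic; 6 months, so m = 60 or 30 visits per provider at 10 or 5 per month; 17% reference rate.

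**Formula** (normal approximation on the log-odds scale, post-intervention data only):

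- Total latent variance = (π²/3)/(1 − 0.075) = 3.557
- Clinic variance = 0.025 × 3.557 = 0.0889; provider variance = (0.075 − 0.025) × 3.557 = 0.1778
- Variance per clinic, V(p) = 0.0889 + 0.1778/10 + 1/(10·m·p(1 − p))
- SE = √(V(p₀)/n₀ + V(p₁)/n₁); power = Φ(|logit p₀ − logit p₁|/SE − 1.96)

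**Step 1: reproduce Exhibit 9.** Take 10 control clinics (Arm 1) against 30 intervention clinics (Arms 2-4). For 4.5 points at 10 visits per month, V(0.17) = 0.1185 and V(0.125) = 0.1219. SE = √(0.01185 + 0.00406) = 0.1262, the log-odds difference is 0.3603, and power = Φ(2.856 − 1.96) = 81.5%.

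| Difference | 10/month: printed | computed | 5/month: printed | computed |
|---|---|---|---|---|
| 4.5 points | 81% | 81.5% | 77% | 77.5% |
| 5 points | 89% | 89.7% | 86% | 86.5% |
| 5.5 points | 95% | 95.0% | 93% | 92.8% |

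The 10 v 30 split is inferred. It was the only split tried that fitted all six cells.

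**Step 2: the claimed range in opioid users.** The log-odds difference is 0.3153 for 4 points (17% v 13%) and 0.1887 for 2.5 points (17% v 14.5%). At 10 visits per month:

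- Exhibit 9's set-up, 4 points: Φ(0.3153/0.1261 − 1.96) = 71%; 2.5 points: Φ(0.1887/0.1259 − 1.96) = 32%.
- A v B, 12 v 12 clinics, 4 points: SE = √((0.1185 + 0.1214)/12) = 0.1414; Φ(0.3153/0.1414 − 1.96) = 61%.

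All set-ups (range is 5 to 10 visits per month):

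| Set-up, reference rate | 2.5 points | 4 points |
|---|---|---|
| Exhibit 9, 10 v 30, 17% | 30-32% | 66-71% |
| Same contrast, 48 clinics, 12 v 36, 17% | 35-38% | 74-78% |
| A v B, 10 v 10, 17% | 21-23% | 49-53% |
| A v B, 12 v 12, 17% | 25-27% | 56-61% |
| A v B, 12 v 12, 12% (assumed) | 40-44% | 82-87% |
| Pooled factorial arms, 24 v 24, 17% | 44-47% | 85-88% |

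For A v B with 12 v 12 clinics at 17%, 80% power needs 4.9 points (10 visits per month) to 5.1 points (5 per month).

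**Step 3: opioid-naive patients.** The same formula with 12 v 12 clinics and 15 to 30 visits per month gives, at 2.5 points, 89-92% at a 7% base and over 99% at 5%. At 4 points it is over 99% at either base. This formula did not reproduce Exhibit 8, so these values rest on the formula and the stated correlations. Exhibit 8 points the same way: its largest effect, a 30% reduction from 7%, is 0.30 × 7 = 2.1 points, printed at 100% power for intervention versus control.

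**The case against.** **Exhibit 9 tests a different contrast.** It compares intervention with control, so the conflict with the sentence is an inference. This stands.

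**A reader might infer that A v B can never have more power than Exhibit 9 shows.** The documents do not support that. In an A v B comparison neither arm need sit at 17%. If one set achieves the plan's own 5-point effect, the reference is 12%, and 4 points then has 82-87% with 12 v 12 clinics. Pooling 24 v 24, as 17.3 does for each main effect, gives 85-88%. But pooling tests each set against its absence, the 12% reading has one set lowering prescribing from 17% to 8%, and neither assumption is attached to the sentence.

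**The planned model uses pre-period data.** Section 17.3 uses 12 months of baseline and takes the arm-by-period interaction as the effect. If clinic and provider effects are perfectly stable, they cancel. The variance per clinic becomes 1/(10·m·p(1 − p)) + 1/(10·2m·p₀(1 − p₀)), and 12 v 12 at 17% gives 67-92% at 2.5 points and 98-100% at 4. Adding 2(1 − r)(0.0889 + 0.0178) for an assumed pre/post correlation r = 0.8, which is not in the documents, gives 37-46% and 77-87%. So Exhibit 9 is a conservative benchmark, and it does not show that the planned analyses in current users are underpowered. It still does not rescue the sentence: even the most favourable case leaves 67% at 2.5 points with 5 visits per month, and 17.2 claims no such gain.

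**The range may mean one value per population,** 2.5 points for naive patients and 4 for users, mirroring the 3.5 and 5 given just before. The text does not say so, and 4 points in users still has 56-61% for 12 v 12 at 17%.

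**No A v B test is planned.** Correct, and it limits the harm: there is no pre-specified null to misread, only an informal comparison.

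**Conclusion.** As an unqualified statement the claim is unsupported for current opioid users and supportable for opioid-naive patients. On Exhibit 9's assumptions (17% rate, correlations 0.025/0.075, post-period only), power in users is about 66-71% at 4 points and 30-32% at 2.5. For a direct 12 v 12 comparison at a 17% reference it is about 56-61% and 25-27%. The 4-point end can exceed 80% under assumptions the sentence does not state. The 2.5-point end stays below 50% in every post-only set-up tabulated here.

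Two limits apply. These are powers for an opioid prescription, as in Exhibit 9, whereas the current-user primary outcome is a three-category taper variable. They also use alpha 0.05; at 0.025, the level implied by the Bonferroni correction across two populations in 17.3, Exhibit 9's set-up gives 56-60% at 4 points. The point concerns a stated power claim and leaves the primary analysis untouched.

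**What to change.** Restrict the sentence to the opioid-naive population, stating the contrast and base rate, and delete the claim for current opioid users.

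If a current-user figure is kept, give it with its contrast, reference rate, clinics per arm, visits per month and analysis model. For example: 56-61% power at 4 points, and about 5 points for 80% power, for A versus B with 12 v 12 clinics, a 17% reference, 5-10 visits per provider per month and post-period data only. The bare percentage should not be inserted without those conditions, because it changes materially with each of them.

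In either case, add that 17.3 plans no test of A against B, so the statement supports no pre-specified analysis.

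The cost is one sentence in 17.2. Design, sample size and primary analysis do not change; one stated power becomes less favourable.

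### Exhibit 8's power figures do not follow from the months 1-6 comparison that section 17.2 describes; they appear to rest on an unstated pre/post basis, different from Exhibit 9's and from the pooled contrast in 17.3

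*Combined protocol and SAP*

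**What the plan says.** Section 17.2 gives one set of assumptions for its power figures. On the test: "All power calculations assume a two-sided test at the 0.05 significance level". On the comparison: "Power for the Primary Aim (comparison of intervention arms to the control during months 1-6"). On size: "assuming a total of 48 clinical are randomized (equal allocation between Arms 1-4) with a conservative estimate of 10 providers per clinic". On clustering: "We assumed the correlation for visits within the same clinic (but with different providers) was 0.025 and the within-provider correlation would be 0.075", with the "correlation given on the logistic scale". It then concludes: "Exhibits 8 and 9 demonstrate that we have sufficient power across a wide range plausible scenarios".

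Two tables follow, each with a single row labelled 0.025/0.075.

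- Exhibit 8: "Power to detect a difference in proportion of eligible visits with an opioid prescription between intervention and control arms". Control rate 7%. For reductions of 15/20/25/30% it gives 96/100/100/100% at 30 eligible visits per provider per month and 76/95/100/100% at 15.
- Exhibit 9: "Power to test a difference in proportion of eligible visits resulting in an opioid prescription between intervention and controls arms in opioid-using population". Control rate 17%, 40 clinics. For differences of 4.5/5/5.5 points it gives 81/89/95% at 10 visits and 77/86/93% at 5.

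The primary analysis in 17.3 is a mixed logistic model on 12 pre-intervention months plus the post-intervention period. It has random effects for clinic and PCP, and the arm-by-period interaction is the effect measure. Each intervention's two arms are pooled against the other two (24 v 24 of 48 clinics). A Bonferroni correction covers the two populations.

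**The concern.** The two exhibits carry the same correlation label and share one description, yet they respond differently to the number of visits. In a comparison of clinics over months 1-6 at these correlations, variation between clinics and providers dominates, so halving visits should cost little power. Exhibit 9 behaves this way (81% to 77%). Exhibit 8 does not (96% to 76%).

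A reader of 17.2 therefore cannot tell which comparison Exhibit 8 describes or what it assumes. If the trial found nothing for the opioid-naive population, a true 15% reduction might be dismissed on the strength of 96% or 76% power that the described comparison does not have, and that the planned comparison has only under a condition the plan does not mention.

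**Working it through.** **Inputs.** From 17.2: two-sided 0.05, 12 clinics per arm, 10 providers per clinic, correlations 0.025/0.075 on the logistic scale. From the exhibits: control rates, visits, effects, and 40 clinics in Exhibit 9. From 17.3: 12 pre-months, interaction, 24 v 24 pooling, Bonferroni (0.05/2 = 0.025). The six post-months follow the months 1-6 wording.

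**Formulas.** Total latent variance = (π²/3)/(1 − 0.075) = 3.557. Clinic part = 0.025 × 3.557 = 0.0889. Provider part = 0.050 × 3.557 = 0.1778. Cluster variance per clinic B = 0.0889 + 0.1778/10 = 0.1067. Visit variance per clinic V = 1/[n p(1 − p)], where n is visits per clinic. Power = Φ(d/SE − z), where d is the absolute log odds ratio.

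**1. Exhibit 9 as months 1-6 only, 10 control v 30 intervention clinics.** SE² = (B + V0)/10 + (B + V1)/30. At 17% v 12.5% and 10 visits, n = 600, V0 = 0.0118, V1 = 0.0152, SE = 0.1262, d = 0.3603, power 81.5%.

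| Visits | Computed | Stated |
|---|---|---|
| 10 | 81.5/89.7/95.0% | 81/89/95% |
| 5 | 77.5/86.5/92.8% | 77/86/93% |

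Exhibit 9 reproduces within 1 point with the full correlation.

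**2. How Exhibit 8 scales with visits.** Powers of 96% and 76% imply d/SE of 3.71 and 2.67, a ratio of 1.39 (1.36-1.42 allowing for rounding), close to √2. In a months 1-6 comparison at the labelled correlation, average V for a 15% reduction is 0.0092 at 30 visits and 0.0185 at 15. The ratio would be √[(0.1067 + 0.0185)/(0.1067 + 0.0092)] = 1.04. The variance that does not shrink with visits would be 11.6 times V; the printed figures allow at most 0.17 times.

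**3. Exhibit 8 read as described (months 1-6 only), 15% reduction.** 7% to 5.95% gives d = 0.1737. For 12 v 12 at 30 visits, SE = √[(0.1067 + 0.0085)/12 + (0.1067 + 0.0099)/12] = 0.139, power 23.9%.

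| Clinics compared | 30 visits | 15 visits |
|---|---|---|
| 12 v 12 | 23.9% | 22.5% |
| 12 v 36 | 33.5% | 31.5% |
| 24 v 24 | 42.4% | 39.8% |
| Stated | 96% | 76% |

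With unlimited visits the ceiling is 25.6% (12 v 12) or 45.3% (24 v 24).

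**4. What does reproduce Exhibit 8.** Take a pre/post interaction with 12 v 12 clinics, 12 pre-months and 6 post-months, and let r be the correlation of a clinic's or provider's effect between periods. Each clinic contributes 2(1 − r)B + Vpre + Vpost. At r = 1 the B term vanishes. With V at 7% throughout, 30 visits give SE² = 2 × (0.00427 + 0.00853)/12 = 0.00213, SE = 0.0462, power 96.4%. At 15 visits SE² doubles and power is 75.8%. The full rows are 96.4/99.9/100/100% and 75.8/95.4/99.7/100%. Keeping the labelled random effects and averaging the binomial information over them gives 96.8/99.9/100/100% and 76.8/95.5/99.6/100%. Arm-specific rates without averaging give 95.6% and 73.6% in the 15% column. The basis is therefore inferred from the fit.

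**5. The planned contrast: 24 v 24, pre/post, arm-specific rates.** Example, 15% reduction, 15 visits, r = 0.9: SE² = [(0.0213 + 0.0085 + 0.0171) + (0.0213 + 0.0085 + 0.0199)]/24 = 0.00403, SE = 0.0635, power 78.2%. The values of r are assumptions; the documents give none. Cells show 30/15 visits.

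| r | 15%, α 0.05 | 15%, α 0.025 | 20%, α 0.05 | 20%, α 0.025 |
|---|---|---|---|---|
| 1.0 | 99.9/95.6% | 99.8/92.2% | 100/99.9% | 100/99.7% |
| 0.9 | 89.7/78.2% | 83.7/69.0% | 99.3/96.2% | 98.5/93.2% |
| 0.8 | 71.9/62.6% | 61.7/51.5% | 93.5/87.5% | 89.1/80.8% |

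**The case against.** A reader might infer that the clinic and provider correlation was simply left out of Exhibit 8. The documents do not support that. In the 17.3 interaction, clinic and PCP effects that stay constant over time cancel from the contrast, so near-halving of information when visits halve is what that model predicts. The labelled random effects can be kept and every cell still reproduces within 1 point.

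A reader might also infer that the trial is underpowered. That does not follow either. With stable effects the planned pooling exceeds every Exhibit 8 figure, and at r = 0.9 the 15-visit result (78%) still meets the stated 76%. The difference of interest in 17.2 is 3.5 points. On the logistic scale that difference has about 100% power even in a months 1-6 comparison of 12 v 12 clinics. On the proportion scale, from a 5% control rate, it has about 79% (12 v 12) to 97% (24 v 24).

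Two further points are fair. The months 1-6 sentence cites Exhibits 2a-b, which looks like an outdated cross-reference, and Exhibit 8's own caption states neither period nor clinic count. Sections 9.1 and 12.1 take in all PCPs of the study clinics, so Exhibit 8 does not set enrolment.

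All of this limits the point without removing it. Exhibits 8 and 9 are the power tables that 17.2 relies on, and its months 1-6 sentence is the only description of the comparison. That description fits Exhibit 9 and not Exhibit 8. The stability that Exhibit 8 needs is not stated, and 12 v 12 is not the contrast planned in 17.3.

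**Conclusion.** The point holds as a fault in how the power is described and in what it silently assumes. Exhibit 8's 96% and 76% for a 15% reduction cannot come from the comparison in 17.2, which would give about 24-42% and 23-40%. They fit a pre/post contrast with perfectly stable clinic and provider effects. Exhibit 9 fits a months 1-6 comparison of one arm against three. Neither is the 24 v 24 interaction of 17.3, and neither uses the Bonferroni level.

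For the planned analysis, exposure is confined to the 15% column: from 99.9/95.6% down to 72/63% at alpha 0.05, and from 99.8/92% down to 62/52% at 0.025, as r falls from 1.0 to 0.8. A 20% reduction stays at or above about 80% throughout. The claim of adequate power over a wide range is therefore unsupported at its lower end, while power for the 3.5-point difference is not called into question.

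This rests on the logistic-scale reading of the correlations, an assumed range for r, and six post-months. Six months suits PMP integration, which section 5.5 opens to all clinics at that mark. For choice architecture it is an assumption, because 5.5 drops the second randomisation.

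**What to change.** In 17.2, recompute Exhibits 8 and 9 on one basis: the pooled pre/post interaction of 17.3, with correlations 0.025/0.075, the Bonferroni alpha of 0.025, and a stated range of between-period correlation for clinic and PCP effects (for example 0.8, 0.9 and 1.0). State the contrast, the periods and the clinic count in each caption, and correct the reference to Exhibits 2a-b. Use one control rate for the opioid-naive population (the text has 5%, Exhibit 8 has 7%) and one clinic count (48 in the text, 40 in Exhibit 9). Replace the sufficiency sentence with the smallest reduction that reaches at least 80% power at each correlation. On Exhibit 8's inputs, a 20% reduction meets that at all three values, while 15% does not at 0.8.

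The cost is one table and one sentence. Some stated figures become less favourable. Nothing changes in trial conduct.
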